TR Istanbul University-Cerrahpaşa ID: [name] The Effectiveness of Motivational Interviewing in Reducing the Use of Household Chemicals and Personal Care Products During Pregnancy Study Protocol: February 5, 2024 Clinical Trial Number: NCT ID not yet assigned

WORKING PROTOCOL	
Title / Date	The Effectiveness of Motivational Interviewing in Reducing the Use of Household Chemicals and Personal Care Products During Pregnancy
Approval of the education officer of the unit(s) where the study will be carried out.	Sile State Hospital Gynecology and Obstetrics Polyclinics
Name and surname of the responsible investigator, e-mail address, mobile phone, signature	[name]. [name] [contact] [name]
Assistant researcher name and surname, e-mail address, mobile phone, signature	[name] [contact] [name]
Assistant researcher name and surname, e-mail address, mobile phone, signature	
Financial agreements between the sponsor, principal investigator or research site	

r

7

main purpose, Secondary purpose, if any hypothesis ( es )	
 
Purpose: The aim of the study is to raise awareness among women about the negative effects of household chemicals and personal care products that they frequently use in their daily lives, on themselves and their babies, through motivational interviewing, and to provide positive behavioral change in women through motivational interviewing.
 
Hypotheses:
 
H0: Motivational interviewing is not effective in reducing the use of domestic chemicals and personal care products by pregnant women.
 
H1: Motivational interviewing is effective in reducing pregnant women's use of domestic chemicals and personal care products.
 

Medical condition/area of treatment investigated	In this study; The aim of the study is to examine the effect of motivational interviewing on reducing the use of household chemicals and personal care products during pregnancy. No treatment will be applied.

of the population to be examined (acceptance and exclusion criteria, age range by gender, termination criteria of the study when necessary) identification of subgroups, if any )	
 
Inclusion Criteria:
 
Being at least 18 years old
 
Education level must be at least primary school
 
Speaking Turkish
 
Having a single pregnancy between the 8th and 40th weeks
 
Using household chemicals and personal care products (any product at least once a week)
 
Exclusion Criteria:
 
Having a psychiatric illness that prevents communication,
 
Having a chronic serious physical health problem
 
Termination of pregnancy for any reason
 
Having a risky pregnancy (preeclampsia, threat of premature birth)
 
Intrauterine growth retardation, having a pregnancy with fetal anomalies
 
Working in a job that requires heavy use of chemicals, such as hairdresser, dry cleaner, beautician.
 

---	---

	Independent variables: Demographic characteristics of women, obstetric characteristics, motivational interviewing Dependent variables: Household Chemicals and Personal Care Products Use Evaluation Form, Self-Efficacy Competence Scale, and Endocrine Disruptors Attitude Scale.
Design features (clinical trial / retrospective study / case) sample size, determination of the number of centers, study duration, if any randomization method and its importance Blindness method and its importance, if any	The research was conducted in a prospective pre-test, post-test based randomized controlled experimental research design.Using the G*Power (3.0.10) Program, the sample size was determined as at least 64 people for each of the experimental and control groups, with 80% power, 0.05 margin of error and 0.5 effect level. Considering the possibility of data loss later on, 70 pregnant women (140 in total) were included in each group. The groups were randomized into 2 groups using a web-based randomization program (http://www.randomizer.org). The researcher included pregnant women who met the inclusion criteria in the outpatient clinics on certain days of the week, in accordance with the randomization process.
Address of the clinic, laboratory, other medical units and institutions, if any, from cases , processing of data/keeping records, evaluation criteria, quality control and quality assurance	No samples will be taken from the pregnant women forming the sample group.
Statistical method to be applied	Analysis of the research data was done with SPSS version 23.0 package program. Descriptive statistics of continuous variables in the study were shown with mean, standard deviation, minimum and maximum values, and descriptive statistics of categorical variables were shown with frequency and percentage. Normality analysis was performed before making comparisons between variables. Since skewness and kurtisos values are between -2 and +2, it is assumed that the variables have a normal distribution (George and Mallery, 2010). Therefore, parametric tests were used in the analyses. While the score differences of the experimental and control groups between groups and time were examined with the t test, the change between groups according to time was examined using mixed pattern analysis of variance - ANOVA (generalized linear model). Cohen-d effect value was used for change over time and between groups, and eta squared ( $\eta$ 2) value was used for change on the group*time axis. Eta

squared is considered as low potency of 0.01, medium potency of 0.06,
and high potency of 0.14 and above.

List of publications: at least 2 (copies will be on file)	Ashrap P, Watkins DJ, Calafat AM, Ye X, Rosario Z, Brown P, Velez-Vega CM, Alshawabkeh A, Cordero JF, Meeker JD. Elevated concentrations of urinary triclocarban, phenol and paraben among pregnant women in Northern Puerto Rico: Predictors and trends. Environ Int. 2018 Dec;121(Pt 1):990-1002. doi: 10.1016/j.envint.2018.08.020. Epub 2018 Oct 11. PubMed ID: 30316544

Summary of findings from studies conducted / supporting information for this study	in 2022, Deierlein et al. Women reported use of personal care and household cleaning products within the previous month, changes in antibacterial product use, receipt of healthcare provider advice, and opinions on environmental chemicals (n = 320). On average, women used 15 personal care products and 7 household cleaning products. Results from this study suggest that women may have increased their product use during the pandemic (Deierlein, L. et al, 2022). in 2018, Ashrap et al. 1003 pregnant women between years 2010 and 2016 from prenatal clinics and collected urine samples and questionnaire data on personal care product use at up to three separate visits, between 16 and 28 weeks gestation. A decreasing temporal trend was statistically significant for urine concentrations of BPA during the study period, while the BPA substitute BPS showed an increasing temporal trend. Significant and positive associations were found between biomarker concentrations with the products use in the past 48-h (soap, sunscreen, lotion, cosmetics). There was an increasing trend of triclocarban/triclosan urinary concentrations with increased concentrations of triclocarban/triclosan listed as the active ingredient in the bar soap/liquid soap products reported being used.Results suggest several potential exposure sources to triclocarban, phenols, and parabens in this population and may help inform targeted approaches to reduce exposure (Ashrap P. et al, 2018).

Publication policy	The research will be carried out in line with universal ethical principles. In order to conduct the research, permission was first obtained from Istanbul University-Cerrahpaşa Non-Interventional Ethics Committee. Participants in the study were given information in the Informed Volunteer Consent form, and their verbal and written consent was obtained. The monitoring and supervision of the study was carried out by the responsible researcher and the thesis advisor.
	by the responsible researcher and the thesis advisor.

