TR Istanbul University-Cerrahpaşa ID: [name] The Effectiveness of Motivational Interviewing in Reducing the Use of Household Chemicals and Personal Care Products During Pregnancy Statistical Analysis Plan: February 5, 2024 Clinical Trial Number: NCT ID not yet assigned

General Hypothesis of the Study

H0: Motivational interviewing is not effective in reducing the use of domestic chemicals and personal care products by pregnant women.

H1: Motivational interviewing is effective in reducing pregnant women's use of domestic chemicals and personal care products.

Independent variables: Demographic characteristics of women, obstetric characteristics, motivational interviewing

Dependent variables: Household Chemicals and Personal Care Products Use Evaluation Form, Self-Efficacy Competence Scale, and Endocrine Disruptors Attitude Scale.

[figure not shown]
Design features

[figure not shown]
The research was conducted in a prospective pre-test, post-test based randomized controlled experimental research design. Using the G*Power (3.0.10) Program, the sample size was determined as at least 64 people for each of the experimental and control groups, with 80% power, 0.05 margin of error and 0.5 effect level. Considering the possibility of data loss later on, 70 pregnant women (140 in total) were included in each group. The groups were randomized into 2 web-based randomization groups using а program (http://www.randomizer.org). The researcher included pregnant women who met the inclusion criteria in the outpatient clinics on certain days of the week, in accordance with the randomization process.

Analysis

Analysis of the research data was done with SPSS version 23.0 package program. Descriptive statistics of continuous variables in the study were shown with mean, standard deviation, minimum and maximum values, and descriptive statistics of categorical variables were shown with frequency and percentage. Normality analysis was performed before making comparisons between variables. Since skewness and kurtisos values are between -2 and +2, it is assumed that the variables have a normal distribution (George and Mallery, 2010). Therefore, parametric tests were used in the analyses. While the score differences of the experimental and control groups between groups and time were examined with the t test, the

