change between groups according to time was examined using mixed pattern analysis of variance - ANOVA (generalized linear model). Cohen-d effect value was used for change over time and between groups, and eta squared (η 2) value was used for change on the group*time axis. Eta squared is considered as low potency of 0.01, medium potency of 0.06, and high potency of 0.14 and above.

Method

The research was conducted in a prospective pre-test, post-test based randomized controlled experimental research design. The sample of the study consisted of 140 pregnant women who applied to the Ministry of Health Istanbul Provincial Health Directorate and Sile State Hospital Gynecology and Obstetrics Polyclinics between May and December 2023, volunteered to participate in the study and met the inclusion criteria.

Firstly, the Informed Consent Form and Introductory Information Form were applied to the women, then the Personal Care Products Use Evaluation Form, Self-Efficacy Scale and Endocrine Disruptors Attitude Scale were applied. The experimental group was informed about the motivational interviewing technique and an appropriate plan was made. After the interviews, the Personal Care Products Use Evaluation Form, Self-Efficacy Scale and Endocrine Disruptors Attitude Scale were re-administered.

SCALES

Dear Participant,

This research; It is carried out by graduate student [name] under the coordination of [name]. [name], one of the faculty members of Istanbul University-Cerrahpaşa Faculty of Health Sciences, Department of Midwifery. In this study, it was aimed to test the effectiveness of motivational interviewing in reducing the use of household chemicals and personal care products during pregnancy.

It is extremely important that you answer this form correctly in order to obtain healthy results in our research. Participation in the study is voluntary. The data obtained from this study will be used in scientific publications and will guide future research, training and consultancy in this field. All information to be collected within the scope of the study will be kept confidential, carefully protected and will be considered only as scientific data Thank you for your support by participating in our research.

[name] Graduate Student [name]. [name] Advisor

PART I- INTRODUCTORY INFORMATION FORM (To be applied only before the interview)

- 1. Your age:
- 2. Your pre-pregnancy weight: Your height:
- 4. Your age at marriage.....

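### An exclusion that can act only after enrolment can remove randomised women; no analysis set is stated, and neither planned analysis adjusts for the pre-test score and gestational week already collected

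*Protocol*

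**What the plan says.** **Eligibility (Protocol, population row).** Inclusion requires "Having a single pregnancy between the 8th and 40th weeks". The exclusions include "Termination of pregnancy for any reason", with no time point. The row's heading asks for acceptance and exclusion criteria and also for "termination criteria of the study when necessary", so the item may have been meant as a withdrawal rule.

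**Size (SAP, Design features; same in the Protocol).** At least 64 per group for 80% power, 0.05 and an effect of 0.5, then: "Considering the possibility of data loss later on, 70 pregnant women (140 in total) were included in each group".

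**Post-test (SAP, Method).** "After the interviews, the Personal Care Products Use Evaluation Form, Self-Efficacy Scale and Endocrine Disruptors Attitude Scale were re-administered". No interval is given. Interviews are described for the experimental group only, so controls have no stated re-test time.

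**Analysis (Protocol, Statistical method; same in the SAP, Analysis).** "While the score differences of the experimental and control groups between groups and time were examined with the t test"; and "the change between groups according to time was examined using mixed pattern analysis of variance". Eta squared is attached to the group-by-time term.

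**Data available.** Gestational week is asked at entry (SAP, Part II). Obstetric characteristics are listed as independent variables in both documents, but no described model contains them.

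**Dates.** Recruitment ran from May to December 2023 (SAP, Method); the plan is headed "Statistical Analysis Plan: February 5, 2024".

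**The concern.** A woman whose pregnancy has already ended fails the inclusion criterion, so the exclusion adds nothing at screening. It does work only once a woman is in the study. A woman entering late may give birth before her post-test. The plan does not say whether she then stays in the analysis, leaves it, or is re-tested after birth. For a woman re-tested after birth, the use form's answer about avoiding a product on account of the pregnancy no longer fits.

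Two things are at stake. First, a reader cannot tell whether the arms compared are the arms as randomised. Secondly, two baseline variables that could sharpen the comparison are collected, yet neither planned analysis uses both as covariates.

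**Working it through.** **1. The plan's own figure.** Read the 0.5 effect as Cohen's d and the test as a two-sided two-sample t-test (neither is stated). With 64 per arm, noncentrality = 0.5 × √(64/2) = 2.83 on 126 df, and power is 80.1%; with 63 it is 79.5%. The stated 64 reproduces. A one-sided test would need 51, so two-sided is the better reading. The implied loss allowance is 6/70 = 8.6% per arm.

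**2. Precision at 70 per arm.** Let r be the pre-post correlation (not in the documents; assumed 0.3 / 0.5 / 0.7), with equal SDs at the two tests.
- t-test on post-test scores: noncentrality 0.5 × √35 = 2.96.
- Group-by-time with two time points equals a t-test on change scores: effective d = 0.5/√(2(1−r)) = 0.423 / 0.500 / 0.645.
- Linear model with pre-test and gestational week, two df fewer: effective d = 0.5/√(1−r²) = 0.524 / 0.577 / 0.700. Week is credited with no gain of its own.

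| Analysis | r = 0.3 | r = 0.5 | r = 0.7 |
|---|---|---|---|
| t-test, post-test scores | 83.6% | 83.6% | 83.6% |
| Group-by-time (or t-test on change) | 69.9% | 83.6% | 96.7% |
| Adjusted model | 86.8% | 92.4% | 98.4% |

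**3. How much loss the allowance covers (illustration).** Assume even entry over the 32-week window, birth at week 40, a post-test k weeks after entry, and equal loss in both arms. If every woman who delivers first is lost, the allowance is used up at 32 × 6/70 = 2.7 weeks. At k = 4, 70 × (1 − 4/32) leaves 61 per arm and 78% power for the post-test t-test; at k = 8, 52 remain and power is 71%. If only half are lost, the threshold is 64 × 6/70 = 5.5 weeks, with 65 per arm (81%) at k = 4 and 61 (78%) at k = 8. An almost immediate post-test would lose few women. At 61 per arm the adjusted model has 82 / 89 / 97% against 64 / 78 / 94% for group-by-time.

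**4. Bias (a different scenario).** With equal loss in both arms, or no effect of gestational week on the score, this mechanism gives zero bias. Suppose instead that only the experimental arm loses its last k weeks of entrants. The SD of entry week is 32/√12 = 9.24, so that arm's mean week shifts by (k/2)/9.24 = 0.217 SD (k = 4) or 0.433 SD (k = 8). With an assumed slope of 0.3 SD per SD of week:
- t-test on post-test scores: 0.3 × shift = 0.065 / 0.130 SD.
- Group-by-time: (post slope − pre slope) × shift, which is 0 if the slopes are equal and 0.065 / 0.130 if week affects only the post-test.
- Adjusted model: 0 in both cases, because the assumed effect is linear.

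For a non-linear effect, assume a 0.5 SD step from week 32. Simulation (6,000 trials per setting, r = 0.5, no true effect) gives these sizes of bias in SD, for k = 4 / k = 8:

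| Step present at | t-test, post-test | Group-by-time | Adjusted model |
|---|---|---|---|
| Post-test only | 0.05 / 0.12 | 0.06 / 0.12 | 0.02 / 0.07 |
| Both tests | 0.06 / 0.13 | 0.00 / 0.00 | 0.01 / 0.04 |

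Neither the ANOVA nor the adjusted model is safer in every case.

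**The case against.** **The plan does not ignore the pre-test.** A reader might infer that the between-arm comparison is a t-test on post-test scores alone. The text does not say so. Its wording fits post-test scores, change scores or within-group change, and the same sentence assigns change between groups to a mixed ANOVA that uses the pre-test. This objection stands. What remains is that the t-test's score is unspecified and neither analysis is baseline-adjusted.

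**No removal is documented.** The SAP says that the sample consisted of 140 women, and neither document says that birth counts as termination. This also stands, although a sample of 140 does not establish that 140 were re-tested or analysed. Two figures near the SAP's design section are not shown, so the absence of an analysis set can be asserted only for the readable text.

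**The adjusted model does not repair the analysis set.** It needs both scores, as the ANOVA does, so it would use essentially the same women. Its advantage is mainly precision. Where gestational week has the same non-linear effect at both tests and only one arm loses women, group-by-time does better. This is correct, and it is why both should be reported.

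**The illustrations rest on assumptions.** The interval, the spread of entry, the pattern of loss and the effect of gestational week are all assumed.

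**Conclusion.** The concern holds in a limited form. The exclusion can remove randomised women if applied as written, and the readable text does not say who is analysed, how births before the post-test are treated, or when each arm is re-tested. Both planned analyses leave precision unused. At 70 per arm the adjusted model gains about 17, 9 and 2 percentage points of power over group-by-time at r = 0.3, 0.5 and 0.7, and about 3, 9 and 15 points over a t-test on post-test scores. These gains rest on d = 0.5, two-sided 5% testing and the assumed r.

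A reader might go further and conclude that the arms compared are not those randomised, or that the result is biased. The documents do not support that: bias needs loss that differs by arm and is related to the outcome, and they show neither. Nor should the two sets of adverse figures be added together. Power of 78% or 71% needs both arms to lose every late entrant, which gives no bias by this route. The 0.065 or 0.130 SD bias needs loss in one arm only, and post-test t-test power is then 80.9% (70 against 61) or 77.3% (70 against 52). The stated sample size is not in error.

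**What to change.** 1. Apply the exclusions only up to randomisation, and analyse every woman who has a post-test in the arm assigned, whatever happened to the pregnancy later.
2. Make the main between-arm comparison a linear model of post-test score on arm, pre-test score and gestational week at entry, and report the mixed group-by-time ANOVA beside it. If the t-test is kept, say which score it compares. Label the model as chosen after data collection, because recruitment ended in December 2023 and the plan is dated February 2024.
3. Report by arm the women removed or without a post-test and the post-tests done after birth. State whether birth was counted as termination and when each arm was re-tested. Add a sensitivity analysis that excludes post-tests done after birth.

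**Cost.** A check of the records and a little analysis on data already held. The adjusted model cannot be presented as pre-specified, and it does not recover women without a post-test. If gestational week has the same non-linear effect at both tests and only one arm loses women, it is off by about 0.01 to 0.04 SD in the illustration above, where group-by-time is not.

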TR Istanbul University-Cerrahpaşa ID: [name] The Effectiveness of Motivational Interviewing in Reducing the Use of Household Chemicals and Personal Care Products During Pregnancy Statistical Analysis Plan: February 5, 2024 Clinical Trial Number: NCT ID not yet assigned

General Hypothesis of the Study

H0: Motivational interviewing is not effective in reducing the use of domestic chemicals and personal care products by pregnant women.

H1: Motivational interviewing is effective in reducing pregnant women's use of domestic chemicals and personal care products.

Independent variables: Demographic characteristics of women, obstetric characteristics, motivational interviewing

Dependent variables: Household Chemicals and Personal Care Products Use Evaluation Form, Self-Efficacy Competence Scale, and Endocrine Disruptors Attitude Scale.

[figure not shown]
Design features

[figure not shown]
The research was conducted in a prospective pre-test, post-test based randomized controlled experimental research design. Using the G*Power (3.0.10) Program, the sample size was determined as at least 64 people for each of the experimental and control groups, with 80% power, 0.05 margin of error and 0.5 effect level. Considering the possibility of data loss later on, 70 pregnant women (140 in total) were included in each group. The groups were randomized into 2 web-based randomization groups using а program (http://www.randomizer.org). The researcher included pregnant women who met the inclusion criteria in the outpatient clinics on certain days of the week, in accordance with the randomization process.

Analysis

Analysis of the research data was done with SPSS version 23.0 package program. Descriptive statistics of continuous variables in the study were shown with mean, standard deviation, minimum and maximum values, and descriptive statistics of categorical variables were shown with frequency and percentage. Normality analysis was performed before making comparisons between variables. Since skewness and kurtisos values are between -2 and +2, it is assumed that the variables have a normal distribution (George and Mallery, 2010). Therefore, parametric tests were used in the analyses. While the score differences of the experimental and control groups between groups and time were examined with the t test, the

change between groups according to time was examined using mixed pattern analysis of variance - ANOVA (generalized linear model). Cohen-d effect value was used for change over time and between groups, and eta squared (η 2) value was used for change on the group*time axis. Eta squared is considered as low potency of 0.01, medium potency of 0.06, and high potency of 0.14 and above.

Method

The research was conducted in a prospective pre-test, post-test based randomized controlled experimental research design. The sample of the study consisted of 140 pregnant women who applied to the Ministry of Health Istanbul Provincial Health Directorate and Sile State Hospital Gynecology and Obstetrics Polyclinics between May and December 2023, volunteered to participate in the study and met the inclusion criteria.

Firstly, the Informed Consent Form and Introductory Information Form were applied to the women, then the Personal Care Products Use Evaluation Form, Self-Efficacy Scale and Endocrine Disruptors Attitude Scale were applied. The experimental group was informed about the motivational interviewing technique and an appropriate plan was made. After the interviews, the Personal Care Products Use Evaluation Form, Self-Efficacy Scale and Endocrine Disruptors Attitude Scale were re-administered.

SCALES

Dear Participant,

This research; It is carried out by graduate student [name] under the coordination of [name]. [name], one of the faculty members of Istanbul University-Cerrahpaşa Faculty of Health Sciences, Department of Midwifery. In this study, it was aimed to test the effectiveness of motivational interviewing in reducing the use of household chemicals and personal care products during pregnancy.

It is extremely important that you answer this form correctly in order to obtain healthy results in our research. Participation in the study is voluntary. The data obtained from this study will be used in scientific publications and will guide future research, training and consultancy in this field. All information to be collected within the scope of the study will be kept confidential, carefully protected and will be considered only as scientific data Thank you for your support by participating in our research.

[name] Graduate Student [name]. [name] Advisor

PART I- INTRODUCTORY INFORMATION FORM (To be applied only before the interview)

- 1. Your age:
- 2. Your pre-pregnancy weight: Your height:
- 4. Your age at marriage.....
- 5. How many years have you been married?.....
- 6. What is your educational background?

()1-Primary school graduate

() 2-Secondary school graduate

() 3-High school

()

graduate 4-University graduate

- 7. Profession
- 1. () 1-Housewife
- 2. () 2-Worker
- 3. () 3-Officer
- 4. Your family structure
 - () 1-Core () 2-Wide () 3- Fragmented

9. Your income status

() 1-Income equal to expenditure () 2-Income more than expenditure () 3-Income less than expenditure

PART II- QUESTIONS ABOUT PREGNANCY

- 1. Your gestational week
- 2.

Number of	Number of Live Births	Number of	Number of Curettages
Pregnancies		Miscarriages	

- 3. Was your pregnancy planned? ()1-Yes ()2-No
- 4. Your status of regular pregnancy follow-ups ()1-Yes ()2-No
- 5. Do you smoke? () 1-Yes (how many per week......) () 2-No () 3-Quit
- 6. Do you drink alcohol? () 1- No () 2-Rarely () 3- Occasionally () 4-Often
- 7. Does your partner smoke? () 1-Yes (how many pieces per week......) () 2-No
- 8. If your spouse smokes, does he smoke next to you? ()1-Yes ()2-No

PART III- QUESTIONS ABOUT THE USE OF HOUSEHOLD CHEMICAL PRODUCTS AND PERSONAL CARE PRODUCTS DURING PREGNANCY

1. How do you make your choices in the use of personal care products during pregnancy (more than one option can be checked)

- 1. I continue to use the products I used before pregnancy
- 2. Being a well-known brand
- 3. Being an organic product
- 4. Recommendation of friends
- 5. Social media recommendation
- 6. Smell
- 7. Economical
- 8. The elegance of its packaging
- 9. The place I bought is reliable
- 10. Their content is safe and clean
- 11. Other (specify.....)
- 1. How do you make your choices in the use of domestic chemical products during pregnancy (more than one option can be checked)
 - 1. I continue to use the products I used before pregnancy
 - 2. Being a well-known brand
 - 3. Being an organic product
 - 4. Recommendation of friends
 - 5. Social media recommendation
 - 6. Good smell or odorless
 - 7. Economical
 - 8. The elegance of its packaging
 - 9. The place I bought is reliable
 - 10. Their content is safe and clean
 - 11. Other (specify.....)
- 2. In your opinion, which personal care products should not be used/reduced during pregnancy?
 - 1. No need to reduce any of them
 - 2. Rinsed products
 - 3. Products that are applied to the skin and are not rinsed
 - 4. Products applied to hair

- 5. Make-up products
- 6. Intimate care products

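### No planned test adjusts for the pre-test score, so a nearly cost-free gain in precision is missed

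*SAP*

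**What the plan says.** The SAP (Method) describes a randomised pre-test/post-test design. The forms are completed before the interviews, and afterwards the use form, "Self-Efficacy Scale and Endocrine Disruptors Attitude Scale were re-administered". Each woman followed up therefore has two measurements per outcome.

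The SAP (Analysis) names two kinds of test, and the Protocol (Statistical method to be applied) has the same text:

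- t tests: "While the score differences of the experimental and control groups between groups and time were examined with the t test";
- a mixed ANOVA: "change between groups according to time was examined using mixed pattern analysis of variance - ANOVA (generalized linear model").

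On effect sizes, "Cohen-d effect value was used for change over time and between groups", with eta squared for group-by-time. Neither document mentions ANCOVA, a covariate or baseline adjustment, and the pre-test score is not among the listed independent variables.

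The sample size (SAP, Design features) is at least 64 per group, "with 80% power, 0.05 margin of error and 0.5 effect level". Enrolment was 70 per group. The text names neither the test nor the SD to which the 0.5 belongs.

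**The concern.** Each planned between-arm test fixes in advance the weight given to the pre-test. The post-test t test gives it weight 0. With two time points, the group-by-time term is the same test as a t test on change scores, which gives it weight 1. ANCOVA estimates the weight from the data, so it usually yields a narrower interval for the difference between arms without any new measurement.

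A second point follows. If 0.5 is in single-score SDs, 64 per group suits a between-group t test, but the same 80% need not hold for the group-by-time result. A reader could wrongly carry it over.

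**Working it through.** **Inputs.** From the SAP (Design features): alpha 0.05, power 80%, effect 0.5, n = 64 per group required and 70 enrolled. Assumed: two-sided testing, numeric scores, equal pre and post SDs, 0.5 in single-score SDs, and r = 0.3, 0.5 or 0.7.

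**The plan's own figure.** For a two-sample t test with d = 0.5, the noncentrality is 0.5 × √(64/2) = 2.83 on 126 df. Power is 80.1%, and 63 per group gives 79.5%, so 64 per group reproduces. A one-sided test would need only 51.

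**Variances, relative to the post-test comparison**

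- Post-test t test: 1.
- Group-by-time (change score): 2(1 − r).
- ANCOVA: (1 − r²) × f, where f = 1 + 1/(2n − 4) allows for chance baseline imbalance. f is 1.0081 at n = 64 and 1.0074 at n = 70.

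On simulated data the group-by-time F equalled the squared change-score t (20.803 for both).

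**Power.** The effect is 0.5 divided by the square root of the variance above. The noncentral t has 2n − 2 df, or 2n − 3 for ANCOVA. For example, at r = 0.5 and n = 64 the ANCOVA effect is 0.5/√(0.75 × 1.0081) = 0.575, which gives 89.8%.

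| n per group | Test | r = 0.3 | r = 0.5 | r = 0.7 |
|---|---|---|---|---|
| 64 | Post-test t | 80.1% | 80.1% | 80.1% |
| 64 | Group-by-time | 66.0% | 80.1% | 95.2% |
| 64 | ANCOVA | 83.4% | 89.8% | 97.5% |
| 70 | Post-test t | 83.6% | 83.6% | 83.6% |
| 70 | Group-by-time | 69.9% | 83.6% | 96.7% |
| 70 | ANCOVA | 86.6% | 92.2% | 98.4% |

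Simulation (40,000 trials per setting, n = 64) agrees: ANCOVA 83.4 / 90.0 / 97.5% and group-by-time 65.7 / 80.2 / 95.2%. Type I error at r = 0.3 was 5.0 to 5.1% for all three tests.

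**Equivalent sample size.** To match ANCOVA with 64 per group, multiply 64 by the variance ratio.

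- Post-test comparison: ratios 1.09 / 1.32 / 1.95, so about 70 / 85 / 124 per group.
- Group-by-time: ratios 1.53 / 1.32 / 1.17, so about 98 / 85 / 75 per group.

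**Gain over the better planned test at each r.** At 64 per group the gain in power is 83.4 − 80.1 = 3.3, 89.8 − 80.1 = 9.7 and 97.5 − 95.2 = 2.3 points. At 70 per group the interval-width ratio is √(0.91 × 1.0074) = 0.957, √(0.75 × 1.0074) = 0.869 and √(0.51 × 1.0074/0.6) = 0.925. The interval is therefore narrower by about 4%, 13% and 7%.

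**Worst case.** ANCOVA loses at most √f times the ratio of the t quantiles: its interval is 1.0041 times as wide at n = 64 and 1.0037 times at n = 70. With equal SDs and n = 64 it breaks even with the post-test comparison at r = 0.09 and with group-by-time at r = 0.98. At r = 0 its power is 79.8%.

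**Where the 80% carries over to group-by-time.** With k = SDpre/SDpost, the effect is 0.5/√(1 + k² − 2rk). Power reaches 80% at these values of r:

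| k | n = 64 | n = 70 |
|---|---|---|
| 0.8 | 0.40 | 0.34 |
| 1.0 | 0.50 | 0.45 |
| 1.2 | 0.60 | 0.56 |

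If 0.5 was meant in change-score SDs, group-by-time has 80.1% at 64 per group for any r, and there is no shortfall.

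**The case against.** The plan contains no error here. Both between-arm tests are valid, the sample size reproduces, and the mixed ANOVA does use the pre-test as a repeated measure. The gain depends on r, which no document gives. The largest equivalent sample sizes (124 and 98) arise only against the weaker planned test at that r. H1 concerns product use, and the text available shows frequency categories for that form with no scoring rule, so figures that assume a numeric score with equal SDs may not fit it. It may also be late: recruitment ran "between May and December 2023", and the SAP of 5 February 2024 already describes the data: "Since skewness and kurtisos values are between -2 and +2, it is assumed that the variables have a normal distribution".

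Most of this stands, and it limits the point to a suggested improvement. It does not remove it. The plan names neither between-arm test as the main one, so a reader cannot count on having the better of the two. ANCOVA costs at most about 0.4% of interval width, whatever r is. The timing decides how ANCOVA must be labelled, not whether it is worth reporting.

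**Conclusion.** The concern holds, as an improvement to consider. No planned test conditions on the pre-test score, although the plan collects it. This is lost precision, not bias. The absence of a covariate and the algebra are certain; the size of the benefit in this trial is not, because r is unknown. At 64 per group the gain over the better planned test is about 10 points of power at r = 0.5, and only 2 to 3 points at r = 0.3 or 0.7. These figures rest on numeric scores, equal pre and post SDs and an effect of 0.5 single-score SDs.

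The stated sample size is correct for an unadjusted between-group t test. Whether its 80% also applies to group-by-time depends on r, on the SD ratio and on the SD unit of the 0.5, none of which the plan states.

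**What to change.** 1. For each outcome analysed as a numeric score, add an ANCOVA of the post-test on group and pre-test. Report the adjusted difference between arms with its 95% CI. Define the score of the use form first.
2. If outcome data had not been seen when the change is made, make ANCOVA the main between-arm test and keep group-by-time as supportive. If they had been seen, which the dates and the wording of the SAP suggest, keep the written analyses and report ANCOVA beside them, labelled post hoc.
3. State that the 80% refers to an unadjusted two-group t test with 64 per group at d = 0.5. Add that, if 0.5 is in single-score SDs, it applies to group-by-time at 64 per group only when r is at least about 0.50 with equal SDs (0.40 to 0.60 for SD ratios of 0.8 to 1.2). If 0.5 was meant in change-score SDs, say so.

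The cost is SAP wording and one further SPSS model per score, plus a scoring rule for the use form. No new data or participants are needed.
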